### Imputation of Partial AE End Dates

- If only the month and year are specified, then use the last day of the month.
- If only the year is specified, then use 31 Dec of that year.
- If the AE resolved and the resolution date is completely unknown, then do not impute the resolution date.

In the event of ambiguity or incomplete data which makes it impossible to determine whether an AE was treatment emergent or not, the AE will be considered as treatment emergent.

With respect to AEs, events with missing intensity will be assumed to be severe. Events with missing relationship to iv BRV per the investigator will be assumed to be related.

Data handling for worsened AEs is provided below. The standard AE eCRF has the outcome of “worsened” to be used when there is an increase in the intensity of an AE. The definition of “worsened” is when the AE is still present but at a heightened intensity. The eCRF instructions dictate to complete a new AE screen with the event term of the worsened event.

Note that the outcome of “worsened” is not allowed terminology within the CDISC standards. In the SDTM.AE, the data is mapped to the outcome “Not Recovered/Not Resolved”. The outcome of “Worsened” will be kept in SDTM.SUPPAE. For subject data listings, the convention will be used to map SDTM terminology of “Not Recovered/Not Resolved”.

#### 4.2.5 Handling of study medication with partial or missing date

No imputation should be performed for missing study medication start dates. This field on the eCRF should not be partial or missing.

For partial or missing date of last dose of study medication, the following imputation rules will be applied for the purpose of calculating overall exposure:

- If the day is missing (but month and year available), impute the last dose date as the earliest of the last day of the month or the date of last contact reported on the trial termination eCRF; if day and month are both missing (only year available), impute the last dose date as the earliest of the last day of the year or the date of last contact on the trial termination eCRF.
- If a subject died and has a partial or missing last dose date, the last dose date is to be set to the date of death. If there is a partial date of last dose and the month/year are prior to the month and year of the date of death, follow partial date imputation rules.
- If the last dose date is completely missing and no information could be obtained from data cleaning exercises, the last dose date should be imputed as the date of last contact according to the study termination eCRF. A review of the data for subjects with completely missing last dose dates should be performed to ensure that the imputation does not result in an unrealistic value for duration of exposure.

Imputed date of last dose dates should only be used for calculation of the duration of exposure. The date as recorded on the eCRF should be presented in subject data listings (no imputed dates should be included in subject data listings).

#### 4.2.6 Handling of epilepsy diagnosis with missing date

Imputation methods should be applied for missing or partial epilepsy diagnosis date.

- If the month and year are available, the diagnosis date will be imputed as the later of the following dates: the first day of the month or the subject's birthdate (imputed DOB if only partial DOB is captured).
- If only a year is available, the later of the following dates will be imputed: 1 Jan of the year or the subject's birthdate (imputed DOB if only partial DOB is captured).
- Completely missing dates will not be replaced, and the corresponding derived variables will be set to missing.

#### 4.2.7 Potential impact of Coronavirus Disease 2019 on dropouts or missing data

The Coronavirus Disease 2019 (COVID-19) pandemic may cause disruption in the conduct of ongoing clinical trials including treatment and study withdrawals, subjects missing study visits, and/or visits being performed remotely instead of at site. Therefore, for subjects enrolled after 30th May 2020, an additional eCRF page will be foreseen. Sites will complete this page in case a subject was impacted by coronavirus during the study. The COVID-19 Impact eCRF page will include the timing and impact of COVID-19, and relationship to COVID-19 (i.e. whether the subject has confirmed/suspected COVID-19 infection, or whether its general circumstances around COVID-19 without infection).

### 4.3 Interim analyses and data monitoring

#### 4.3.1 DMC meetings

[figure not shown]
Data will be presented to and reviewed by a DMC during the course of the study. For the first age cohort, after the first half of the subjects receive the 15-minute infusion(s), the DMC will meet to review safety (as indicated in the DMC charter) and, as available, PK data. For subsequent cohorts, the DMC will review data for bolus infusions of the previous cohort and the 15-minute infusions of the current cohort. The DMC will meet no less than approximately every 6 months commensurate with enrollment. The DMC members will be defined in the DMC charter.

At each DMC meeting, the DMC will make recommendations regarding study aspects including:

- Continuation of the study as planned
- Modification of the study or particular expansion cohort(s)
- Suspension of the study or particular expansion cohort(s)

Age cohorts for enrollment are detailed in the schematic in Figure 5-1. Notably, the schematic of sequential cohort enrollment (Figure 5-1) differs from the one provided in the protocol. Ages were changed from “≥12 years to ≤16 years” to “≥12 years to <16 years”, “≥6 years to ≤12 years” to “≥6 years to <12 years” and “≥2 years to ≤6 years” to “≥2 years to <6 years”. This difference is because the protocol has age boundaries of sequential cohort enrollment defined differently in the schematic to the text, but in practice sites have enrolled using the text.

Figure 5-1: Schematic of sequential cohort enrollment during the iv PK Period

DMC=Data Monitoring Committee; inf=infusion; iv=intravenous; PK=pharmacokinetic

### 4.3.2 Interim analysis

No formal interim analysis was planned in this study. The last planned DMC occurred after all subjects aged 2 to <6 years had completed the study, and all subjects aged 1 month to <2 years on 15-minute infusion had completed the study, and the recommendation was to continue the study. However, enrollment was temporarily stopped due to the impact of COVID-19. Therefore, all outputs will be delivered twice, firstly an interim CSR using all data from subjects aged 2 to <6 years and subjects aged 1m to <2 years on 15-min infusion to support ongoing submission work, and secondly a final CSR using all subjects.

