### 2.3 Study design and conduct

EP0065 is a Phase 2 multicenter, open-label study to evaluate the PK, safety, and tolerability of iv BRV administered as a 15-minute iv infusion and an iv bolus (up to 2-minute infusion) in subjects  $\geq 1$  month to  $< 16$  years of age with epilepsy.

Study medication is defined by iv infusion of BRV administered as a 15-minute iv infusion or an iv bolus (up to 2-minute infusion). Oral BRV can be administered during EP0065 but will not be considered as study medication for EP0065.

Approximately 50 enrolled subjects will receive iv BRV in the following age-based cohorts (approximately 12 subjects/cohort):

- Cohort 1:  $\geq 12$  to  $< 16$  years
- Cohort 2:  $\geq 6$  years to  $< 12$  years
- Cohort 3:  $\geq 2$  to  $< 6$  years
- Cohort 4:  $\geq 1$  month to  $< 2$  years

The age at Screening Visit will be the determining factor for age cohort assignment. Each age cohort will have approximately 50% of subjects with iv BRV infusion and 50% with bolus BRV.

The following subjects will be eligible for enrollment in EP0065:

- Open-label BRV (OLB) subjects: currently receiving oral BRV as participants in a long-term, open-label study
- Prescribed BRV (RxB) subjects: currently receiving prescribed oral BRV from commercial supply
- Initiating Oral BRV (IOB) subjects: not currently receiving BRV; first dose of BRV in EP0065 will be oral tablet or solution
- Initiating iv BRV (IIB) subjects: not currently receiving BRV; first dose of BRV in EP0065 will be by iv Infusion

For OLB and RxB subjects, the maximum BRV dose is 5mg/kg/day (rounded). For IOB and IIB subjects, the maximum BRV dose is 4mg/kg/day. Throughout the study, no subject may receive a dose greater than BRV 200mg/day. Subjects will receive oral BRV (tablets or oral solution) in equally divided doses; BRV oral solution may be given by enteric administration (eg, by feeding tube) based on subject need.

The EP0065 study periods and visits are described below. The PK assessments will be made during the iv PK Period only and safety data will be collected throughout the study, with intensive collection of safety data with each iv BRV dose administered. A Schedule of Study Assessments is provided in the protocol for the Screening through iv PK Periods and for the Down-Titration Period and Safety (BRV-free) Periods (for subjects not continuing BRV).

- Screening Period (1 to 10 days)

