After subjects have completed PK sampling with 2 iv BRV infusions, the Investigator may adjust the BRV dose, but the adjusted dose must not exceed 5mg/kg/day (rounded) for OLB and RxB subjects and 4mg/kg/day for IOB and IIB subjects (with the maximums not to exceed 200mg/day). During the iv PK Period, BRV may only be administered intravenously. Enrollment will be sequential by descending age beginning with age-based Cohort 1. For each age cohort, the first half will receive the 15-minute infusion. The Data Monitoring Committee (DMC) will then meet to review safety and, as available, PK data. After the DMC safety review, the remaining half in that age cohort will receive iv BRV as a bolus (up to 2-minute infusion) and the next age cohort may begin the 15-minute infusion. Subjects may receive bolus infusions only after subjects in the preceding age cohort have completed bolus infusions and the DMC have reviewed these data. The DMC will meet no less than approximately every 6 months commensurate with enrollment.

Telephone contact (TC)-1 will occur 1 to 3 days after completing the final iv BRV dose in the iv PK Period to facilitate reporting of infusion-site related AEs.

- Down-Titration Period (up to 4 weeks) and Safety (BRV-free) Period (2 weeks)

Subjects who receive  $\geq 4$  doses of BRV during either the IOB Treatment Period or the iv PK Period and who do not plan to continue treatment with BRV or who discontinue from the study will enter a Down-Titration Period. Subjects who have received  $< 4$  doses of BRV may have BRV down titrated at the discretion of the Investigator. During the Down-Titration Period, subjects will have their BRV dose reduced by a maximum of half the dose every week for a maximum of 4 weeks until a dose of 1mg/kg/day (50mg/day for subjects with body weights  $\geq 50$ kg) is reached. Subjects not able to receive oral BRV for down titration, may receive iv BRV for down titration. In the latter circumstance, the subjects may receive more than 10 consecutive doses of iv BRV in accordance with the Investigator's discretion. A 2-week Safety (BRV-free)

Period will follow the final dose of BRV. In this SAP, the Down-Titration period is considered part of the Follow-Up period, which is described more in [Section 3.2.4](#).

Safety assessments will be collected throughout these periods.

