## 2.4 Determination of sample size

The primary objective of the study is to evaluate the PK, safety, and tolerability of BRV given intravenously. The plan for approximately 50 enrolled subjects (4 age cohorts of approximately 12 subjects each) to receive iv BRV was deemed clinically appropriate for the evaluation of the PK, safety, and tolerability of iv BRV administration in subjects  $\geq 1$  month to  $< 16$  years of age with epilepsy. No formal sample size calculation has been performed.

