## 3 DATA ANALYSIS CONSIDERATIONS

### 3.1 General presentation of summaries and analyses

Statistical analysis and generation of tables, figures, subject data listings, and statistical output will be carried out using SAS Version 9.3 or higher. All summaries will be descriptive; no statistical hypothesis testing is planned. All tables and listings will use Courier New font size 9.

Tables, figures and listings (TFL) will be displayed for the defined analysis sets. If the Safety Set (SS) and the Safety Set-iv (SS-iv) consist of the same number of subjects, TFLs will only be presented for the SS-iv.

For categorical parameters, the number and percentage of subjects in each category will be presented. The denominator for percentages will be based on the number of subjects appropriate for the purpose of the analysis. Unless otherwise noted, all percentages will be displayed to 1 decimal place. No percentage will be displayed for zero counts, and no decimal will be presented when the percentage is 100%.

For continuous parameters, descriptive statistics will include number of subjects (n), mean, standard deviation (SD), median, minimum, and maximum, unless otherwise stated.

Decimal places for descriptive statistics will always apply the following rules unless otherwise stated:

- “n” will be an integer
- Mean, SD, geometric mean, and median will use 1 additional decimal place compared to the original data
- CV [%] will be presented with 1 decimal place
- Minimum and maximum will have the same number of decimal places as the original value

However, the maximum number of decimals displayed will not exceed 4.

All summaries, unless otherwise stated, will be presented overall for all subjects, by age cohorts (Cohort 1:  $\geq 12$  to  $< 16$  years, Cohort 2:  $\geq 6$  years to  $< 12$  years, Cohort 3:  $\geq 2$  to  $< 6$  years, Cohort 4:  $\geq 1$  month to  $< 2$  years), and by infusion duration (15-minute iv infusion and iv bolus (up to 2-minute infusion)). Selected tables will be provided in addition by subject groups (OLB, RxB and IOB combined, and IIB), or by scheduled assessment timepoints as defined in [Section 4.8](#).

Selected summaries will be repeated by the country of enrollment (Hungary and rest of the World).

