## 6 DEMOGRAPHICS AND OTHER BASELINE CHARACTERISTICS

### 6.1 Demographics and other Baseline Characteristics

Demographic variables will be presented for the SS-iv and the SS. The variables to be presented are:

- Age at entry into EP0065 (in years for subjects aged >2 years at study entry, in months for subjects aged ≤ 2 years at study entry)
- Age at first diagnosis (in years and in months) (as defined in [Section 3.2.7](#))

- Duration of epilepsy (in years and in months) (as defined in [Section 3.2.8](#) )
- Categorized age at entry into EP0065:
  - EudraCT age categories:  $\geq 1$  month to  $< 24$  months,  $\geq 24$  months to  $< 12$  years,  $\geq 12$  to  $< 16$  years
  - Age categories for submission:  $\geq 1$  month to  $< 4$  years,  $\geq 4$  to  $< 16$  years
- Gender (male, female)
- Subject group (OLB, RxB, IOB, and IIB)
- Weight at Screening (kg)
- Weight at baseline (kg)
- Weight group at baseline ( $< 50$  kg,  $\geq 50$  kg)
- Height at Screening (cm)
- BMI at Screening ( $\text{kg}/\text{m}^2$ ) (as defined in [Section 3.3](#))
- Racial group (American Indian/Alaskan Native, Asian, Black, Native Hawaiian or Other Pacific Islander, White, Other/Mixed)
- Ethnicity (Hispanic or Latino or Not Hispanic or Latino)
- Country (Countries may include Czech Republic, France, Germany, Hungary, Italy, Ireland, Mexico, Poland, Spain, USA)
- VNS Status (VNS not used, VNS used; if used: VNS active, VNS not active)

The following listings will be provided by age cohort for all subjects screened:

- demographics at Screening
- childbearing potential at Screening
- historical seizure count (describing the type and number of seizures experienced in the 3 weeks prior to Screening)
- diagnosis of epilepsy (describing the primary disease, date of first epilepsy diagnosis and history of status epilepticus prior to the 1-month period before Screening)
- vagus nerve stimulation status at Screening
- family medical history (family medical history is only collected for subjects with potential drug-induced liver injury and will describe the medical conditions including start and stop dates)
- lifestyle (lifestyle information is only collected for subjects with potential drug-induced liver injury and will describe the alcohol- and illicit drug use within past 6 months)

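### SAP 4.3.2 limits the interim CSR to ages 2 to <6 years plus the 15-minute half of Cohort 4, which leaves out Cohorts 1 and 2 and is probably a slip for 2 to <16 years

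*SAP*

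**What the plan says.** SAP 4.3.2 states that no formal interim analysis was planned, but that the pause in enrolment leads to two deliveries: "all outputs will be delivered twice". The first is "firstly an interim CSR using all data from subjects aged 2 to <6 years and subjects aged 1m to <2 years on 15-min infusion". The rest of the sentence gives its purpose and the content of the second: "to support ongoing submission work, and secondly a final CSR using all subjects".

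Other parts of the current SAP bear on who should be in the first delivery:

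- SAP 2.3 sets the order of recruitment: "Enrollment will be sequential by descending age beginning with age-based Cohort 1". Within a cohort, the 15-minute half comes before the bolus half. A cohort's bolus dosing waits until the preceding cohort's bolus dosing is finished and the DMC has reviewed it.
- SAP 3.1 sets the layout: "All summaries, unless otherwise stated, will be presented overall for all subjects, by age cohorts". It then lists four cohorts: 12 to <16, 6 to <12, 2 to <6, and 1 month to <2 years.
- SAP 6.1 has an item headed "Age categories for submission", with two bands: 1 month to <4 years and 4 to <16 years.

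**The concern.** The interim CSR is the report tied to submission work, and its population is set by this single sentence. Read as written, the sentence excludes everyone aged 6 to <16 years. No other operative text adds them back, and no separate earlier report covering them is described.

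A programmer who follows 4.3.2 would drop the two oldest cohorts. One who follows 3.1 and 6.1 would expect them to be present. The SAP therefore supports two different interim datasets, and the narrower one would leave the first report without any PK or safety summary for more than half of the planned subjects who should by then have been dosed.

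**Working it through.** **Step 1. Map the sentence to cohorts.** Ages 2 to <6 years is Cohort 3. Ages 1 month to <2 years on 15-minute infusion is half of Cohort 4. Cohorts 1 and 2 are absent.

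**Step 2. Check whether Cohorts 1 and 2 had been dosed.** SAP 4.3.2 says that all subjects aged 2 to <6 years had completed the study by the last planned DMC meeting, which includes the Cohort 3 bolus half. Under the gating in SAP 2.3, Cohort 3 bolus dosing required Cohort 2 bolus dosing to be complete, and that in turn required Cohort 1 bolus dosing to be complete. In each cohort the 15-minute half precedes the bolus half. If the gating was followed, both halves of Cohorts 1 and 2 had finished iv dosing.

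**Step 3. Set the restriction beside the planned outputs.**

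| Planned output | Content if 4.3.2 is followed as written |
|---|---|
| Summaries by four cohorts (SAP 3.1) | Cohort 1 and 2 columns empty |
| Submission category 4 to <16 years (SAP 6.1) | Ages 4 to <6 years only |
| EudraCT category 12 to <16 years (SAP 6.1) | Empty |
| PK and exposure at 50 kg or more (SAP 9.1, 10.1) | Expected to be empty |
| C-SSRS listing, collected from age 6 (SAP 10.5.8) | Empty or nearly so |

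These displays fit a population running to 16 years.

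**Step 4. Count on planned sizes.** Inputs: "The plan for approximately 50 enrolled subjects (4 age cohorts of approximately 12 subjects each) to receive iv BRV" (SAP 2.4) and "Each age cohort will have approximately 50% of subjects with iv BRV infusion and 50% with bolus BRV" (SAP 2.3).

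- Planned total: 4 × 12 = 48, consistent with the stated figure of approximately 50.
- Half of one cohort: 12 / 2 = 6.
- Should have been dosed at the interim cut: 12 + 12 + 12 + 6 = 42, or 42/48 = 87.5% of the planned total.
- Kept as written: 12 + 6 = 18, or 18/48 = 37.5%.
- Left out: 12 + 12 = 24, and 24/42 = 57% of those who should have been dosed.

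**Step 5. Sensitivity to cohort size.** For equal cohorts of size c, the text keeps 1.5c, omits 2c, and 3.5c are available. The share omitted is 2/3.5 = 57% whatever c is. Taking c = 50/4 = 12.5 instead of 12 gives 18.75 kept, 25 omitted and 43.75 available. Unequal actual cohorts would change the share, and the documents do not give actual enrolment.

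**The case against.** The strongest reply is that nobody chose this population. The preceding sentence of 4.3.2 describes the last DMC milestone in almost the same age terms, so its wording may simply have been carried over, or one digit was lost. The SAP's change list for version 4.0 (section 13.3) describes this same section with an upper age of 16. A difference between a change list and the current text is not itself an error, and the point does not rest on it, but it fits the view that the wider population was meant. This reply stands: the defect is best treated as an internal inconsistency, not a considered analysis decision.

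Three stronger readings are tempting, and the documents do not support them.

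- A reader might infer that data on older children are discarded. They are not: the same sentence promises a final CSR on all subjects. At worst, reporting of Cohorts 1 and 2 is deferred.
- A reader might infer that the submission would have nothing on ages 6 to <16 years. The documents do not say what the submission work covers, or whether the older cohorts' data reach it by another route.
- A reader might turn 18 versus 42 subjects into a loss of precision. For example, the one-sided 95% upper bound for an adverse event never observed is 1 − 0.05^(1/18) = 15.3% against 1 − 0.05^(1/42) = 6.9%. No such bound is planned. Adverse events are reported as counts and percentages, so these figures do not describe any analysis in the SAP.

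It can also be said that the displays in 3.1 and 6.1 are shared by both deliveries and will all be filled in the final CSR. That is true. Their value here is as evidence that the stated age range is probably wrong, not as a separate fault.

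**Conclusion.** The point holds as an inconsistency in a stated analysis population. SAP 4.3.2 as written excludes Cohorts 1 and 2 from the interim CSR, while the rest of the current SAP is laid out for a population running to <16 years. The most plausible explanation is <6 written for <16.

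On planned sizes, about 24 of about 42 subjects would be missing from the interim report. This assumes equal cohorts of about 12, an even split by infusion duration, and gating followed as described. It is a planned count, not an observed one.

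The consequence is confined to the interim CSR. The final CSR is unaffected, and with no hypothesis testing planned there is no error-rate consequence. It still deserves correction, because the affected report is the one linked to submission and the sentence would be programmed as it stands.

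**What to change.** Reword the sentence in SAP 4.3.2 so that the interim CSR population is all subjects aged 2 to <16 years (Cohorts 1 to 3, both infusion durations) plus the subjects of Cohort 4 who received the 15-minute infusion. Naming the cohorts and infusion durations, as well as the ages, would prevent the same slip.

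If a report on the younger children alone is really intended, the SAP should say so and give the reason.

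The cost is one sentence in the SAP. No new data are needed, and the final analysis does not change.
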